**Table 1-1 Objectives and related endpoints**

Objective	Endpoint	Analysis
Primary		
To evaluate long term safety data	Frequency and severity of AEs/SAEs	Refer to Section 2.5 & 2.8
Secondary		
To evaluate clinical benefit as assessed by the investigator	Proportion of patients with clinical benefit as assessed by the investigator at scheduled visits	Refer to Section 2.7

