## **2 Statistical methods**

### **2.1 Data analysis general information**

Data will be analyzed by Novartis using SAS Version 9.3. Only data reported in the database of this protocol will be included in the analyses. Patient data from the parent study will not be taken into account.

Summary tables will be provided for patient disposition, demographic data and treatment exposure. All data collected on the database will be listed, using all patients enrolled in this study.

Categorical data will be presented as frequencies and percentages. For continuous data, mean, standard deviation, median, minimum, and maximum will be presented, unless otherwise stated.

The original protocol was released on 07-Dec-2012. Protocol amendment 1 (PA1) was released on 18-Mar-2016. In this amendment the primary endpoint was changed to safety to better characterize the long-term safety of the compound. In addition, the protocol has been amended to include the collection of all AEs (including non-serious AEs) and an investigator attestation of continued clinical benefit. Additional eCRFs were added to collect data related to

- Investigator attestation of clinical benefit at every quarterly visit
- All adverse events (based on original protocol only SAEs were collected and all SAEs were only collected in ARGUS safety database)
- Relevant medical history/current medical conditions
- Monthly at home pregnancy testing for female patients of child bearing potential (serum/urine)
- Study evaluation completion at the end of the 30 day safety follow up
- Related imaging, drug use 6 months prior to liver event, pathology, medical history possibly contributing to liver dysfunction, local laboratory results (viral serology, autoimmune, immunoglobulin, liver function tests), overview, potential impact of alcohol use, acetaminophen/paracetamol pertaining to liver event (only when drug-induced liver injury (DILI) cases occur)

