## **2.8 Safety analyses**

The assessment of safety will be based mainly on the frequency of AEs and SAEs.

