### **Analysis set and grouping for the analyses:**

The overall observation period will be divided into two mutually exclusive segments:

1. on-treatment period: from day of first dose of study medication in the roll-over study to 30 days after last dose of study medication

2. post-treatment period: starting at day 30+1 after last dose of study medication.

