### 2.8.1 Exposure to study treatment

Exposure will be assessed for both Everolimus and Everolimus + Sandostatin LAR.

The following analyses will be performed to assess study treatment exposure:

- Duration of study drug exposure in years;
- Cumulative dose;
- Actual dose intensity;
- Dose adjustments and discontinuation;

Separate table and plot for on-treatment period and AEs/SAEs collection period in clinical database on patient level will be generated to reflect the proportion of safety data collection within the overall treatment period.

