  - AEs resulting in dose adjustment or interruption regardless of study drug relationship by primary system organ class and preferred term
  - AEs requiring additional therapy and concomitant medication regardless of study drug relationship by primary system organ class and preferred term
  - AESIs regardless of study treatment relationship
    - c. by primary system organ class, preferred term and maximum CTC grade
    - d. by primary system organ class and preferred term
  - AESIs suspected to be study treatment related
    - c. by primary system organ class, preferred term and maximum CTC grade
    - d. by primary system organ class and preferred term
  - AESIs leading to study drug discontinuation regardless of study drug relationship by primary system organ class and preferred term
  - AESIs resulting in dose adjustment or interruption regardless of study drug relationship by primary system organ class and preferred term
  - AESIs requiring additional therapy and concomitant medication regardless of study drug relationship by primary system organ class and preferred term
- SAEs after protocol amendment
  - SAEs regardless of study treatment relationship by primary system organ class and preferred term
  - SAEs suspected to be study treatment relationship by primary system organ class and preferred term

For legal requirements of ClinicalTrials.gov and EudraCT, two required tables on treatment-emergent non-serious AEs with an incidence greater than 5% in clinical database, and on-treatment deaths and treatment-emergent SAEs in ARGUS safety database will be provided by

system organ class and preferred term using the safety set. The rule for the calculation of the number of occurrences is detailed in the Appendix section 5.2.

All of these tables will display the number and percent of patients that experience the given event and will display events by MedDRA. Events will be displayed alphabetically for SOC and PT. All safety data (including those from the post-treatment periods) will be listed and those collected during the post-treatment period are to be flagged. The following listings will also be generated:

- Listing of AEs leading to study drug discontinuation
- Listing of AEs leading to dose adjustment or interruption
- Listing of SAEs in ARGUS safety database
- Listing of SAEs in RDC clinical database

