For each specified AESI, the number and percentage of patients with at least one event of the AESI occurring during the on-treatment period will be summarized. Summaries of these AESIs will be provided grouped by CTCAE grades, relationship, leading to treatment discontinuation, resulting in dose adjustment/interruption, etc.

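### The primary safety tables give percentages with no time at risk, and the RDC percentages would count patients who left before AE collection began

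*SAP*

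**What the plan says.** SAP Table 1-1 sets the primary endpoint as "Frequency and severity of AEs/SAEs", under an objective of evaluating long-term safety. Section 2.8 adds: "The assessment of safety will be based mainly on the frequency of AEs and SAEs".

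The statistic is fixed in three places:
- SAP 2.1, as the general rule: "Categorical data will be presented as frequencies and percentages".
- SAP 2.8.2, for the AE and SAE tables: "All of these tables will display the number and percent of patients that experience the given event".
- SAP 2.8.2.1, for each AESI: "the number and percentage of patients with at least one event of the AESI occurring during the on-treatment period will be summarized".

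Some RDC tables also break down by maximum CTC grade. The two registry tables count occurrences ("The rule for the calculation of the number of occurrences is detailed in the Appendix section 5.2"). Handling of censoring and discontinuation for the primary objective is marked not applicable (2.5.3), and no supportive analysis is planned (2.5.4).

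The risk window is specific to each patient: "on-treatment period: from day of first dose of study medication in the roll-over study to 30 days after last dose of study medication". Treatment is open-ended (SAP 1.1), in a study the protocol expects to keep open for up to 10 years (Protocol 4.1).

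SAP 2.8.1 summarises exposure in years and plans a display of observation time: "Separate table and plot for on-treatment period and AEs/SAEs collection period in clinical database on patient level will be generated". Neither is combined with the event counts.

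The Safety Set is the only analysis set (SAP 2.2). SAP 2.8.2 applies 18-Mar-2016 as a general cutoff for RDC safety data but names no reduced denominator for the RDC tables. The ARGUS SAE tables cover the whole study.

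**The concern.** Two separate problems follow.

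**Time at risk.** The proportion of patients with at least one event depends on the event rate and on how long each patient was observed. When observation is open-ended and unequal, the proportion does not correspond to risk at 1, 3, 5 or any other number of years. The study exists to characterise long-term safety, and its main tables would not say over what length of observation a percentage applies.

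**Denominator of the RDC tables.** Eleven patients had discontinued before the amendment introduced full AE collection. If they stay in the denominator, they are counted as event-free when their AEs were not being recorded. Every RDC percentage, including Grade 3-4 AEs and AESIs, is then too low as a description of the patients actually observed.

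**Working it through.** The plan gives no event rate, follow-up distribution or target, so there is no figure of its own to reproduce. The checks below use its counts and dates, and the assumptions are marked.

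**1. Patient counts (SAP 2.1).** 21 ongoing + 11 discontinued = 32 enrolled at the amendment, and 34 - 32 = 2 consented later. At most 21 + 2 = 23 patients (23/34 = 68%) could contribute RDC events. This assumes that the 11 were already more than 30 days past last dose at the cutoff. The documents do not say that all 21 ongoing patients moved to the amended collection, so the number could also be lower.

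**2. Calendar limits (365.25 days per year).** Dates are the study opening, 13-May-2013 (Protocol, Amendment 01 rationale), the amendment, 18-Mar-2016, and the latest SAP update, 09-Jun-2020 (SAP document history).
- Opening to amendment: 1,040 days = 2.85 years, the most any of the 11 could have had on study.
- Opening to SAP update: 2,584 days = 7.07 years, the most any patient could have had by then.
- Amendment to SAP update: 1,544 days = 4.23 years, the longest possible RDC window by then.

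These are upper limits to a document date, not observed follow-up.

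**3. RDC denominator.** SAP 2.1 reports that about 30% of enrolled patients had AEs in RDC after the amendment; 0.30 × 34 = 10.2, so 10 is a reasonable illustrative count.

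| Patients with event | Of 34 (exact 95% CI) | Of 23 (exact 95% CI) |
|---|---|---|
| 10 | 29.4% (15.1 to 47.5) | 43.5% (23.2 to 65.5) |
| 0 | 0% (upper limit 10.3) | 0% (upper limit 14.8) |

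Using 34 instead of 23 multiplies every percentage by 23/34 = 0.68. It does not change which events pass the registry table's threshold of more than 5%: one patient is below it in both cases (1/34 = 2.9%, 1/23 = 4.3%) and two are above it (5.9%, 8.7%).

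**4. How far a crude percentage depends on follow-up.** Assume a constant hazard h. The chance of at least one event by time t is 1 - exp(-ht), and the expected crude percentage is its mean over patients. The hazards and follow-up mixes are assumptions.

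| Follow-up of 34 patients | h = 0.05/year | h = 0.10/year | h = 0.20/year |
|---|---|---|---|
| 11 at 0.25 y, 23 at 3 y | 9.8% | 18.3% | 32.1% |
| 11 at 0.5 y, 12 at 3 y, 11 at 7 y | 15.3% | 27.0% | 43.4% |
| 11 at 1.5 y, 23 at 5 y | 17.3% | 31.1% | 51.1% |
| True 5-year risk | 22.1% | 39.3% | 63.2% |

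With the hazard held fixed, the percentage moves by a factor of about 1.6 to 1.8 across these mixes, and in each it is below the 5-year risk.

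**5. The same percentage at different rates.** Rate = patients with a first event / patient-years at risk. Ten of 34 is 29.4% in every row. The exact Poisson 95% limits for a count of 10 are 4.80 and 18.39, divided here by patient-years.

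| Assumed mean time at risk | Patient-years | Rate per 100 patient-years (95% CI) |
|---|---|---|
| 1 y | 34 | 29.4 (14.1 to 54.1) |
| 2 y | 68 | 14.7 (7.1 to 27.0) |
| 5 y | 170 | 5.9 (2.8 to 10.8) |

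**The case against.** The endpoint is defined as frequency and severity, not as risk by a stated time. The study is single-arm, tests no hypothesis and has no statistical basis for its size. In that setting n (%) is a valid description of what was observed, and the SAP never says it will be read as long-term risk. ARGUS and RDC results are reported separately and labelled by period. Exposure, the patient-level collection display and full listings give a reader of a 34-patient study a good deal of context. All of this stands.

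A reader might infer that the tables cannot be interpreted at all, or that some patients were followed for only weeks. The documents support neither. The percentages are interpretable as observed frequencies, and no follow-up distribution is given, only calendar limits. It would also be too strong to say that n (%) is the sole content, since grade and occurrence counts appear in some tables; these are not adjusted for time.

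A rate is not a full cure. One rate per 100 patient-years assumes a constant hazard. Parent-study data and exposure are excluded (SAP 2.1, 2.4.1), so the denominator is roll-over time, not total everolimus exposure. For patients enrolled before the amendment, the first RDC event is only the first one recorded after collection began. These limits have to be stated with the rates.

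What the objection does not answer is the RDC denominator, which is wrong even for pure description, and the absence of any link between events and time at risk. Rates and intervals are themselves descriptive and need no hypothesis. The planned exposure summaries do not let a reader derive time at risk for a particular event.

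**Conclusion.** The point holds as a recommended change, not as a fatal flaw. The planned percentages are sound as description but do not estimate long-term risk, because time at risk is unequal and is never used.

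Followed as written, the RDC percentages would be diluted by the 11 patients who had left before AE collection: 29.4% instead of 43.5% for ten patients with an event. That size rests on all 34 enrolled patients being in the Safety Set, on the SAP's silence meaning the full set is the RDC denominator, and on the 11 being past their 30-day window. The count of ten is illustrative.

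The dependence of the percentages on follow-up is shown under assumed constant hazards and follow-up mixes. The direction is certain; the actual size cannot be computed from the documents.

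**What to change.** In SAP 2.8.2:

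1. **RDC denominator.** Base RDC AE tables on Safety Set patients still under observation (first dose to 30 days after last dose) on or after the start of their AE collection. State that number in each table. Define each patient's collection start explicitly, since 2.8.1 needs it but only the global date is given.
2. **Rates beside n (%).** Add patient-years at risk and first-event rates per 100 patient-years with exact Poisson 95% CI:
   - SAEs from ARGUS, with time from the first roll-over dose.
   - Any AE, Grade 3-4 AEs and AESIs from RDC, with time from the later of the first roll-over dose and that patient's start of AE collection.
   - Time ends at the first event or 30 days after last dose, or at the data cutoff for anyone still under observation.
3. **Stated limits.** Note the wide intervals with about 34 patients, the constant-rate assumption, the exclusion of parent-study exposure, and that a first event in RDC means the first recorded after collection began.

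The cost is SAP text and a few table columns. Dosing and AE dates are already collected. One further rule is needed: SAP 5.1.2 marks AE date imputation as not applicable, so partial AE start dates would leave time to first event undefined.

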### **2.8.2.1 Adverse events of special interest / grouping of AEs**

Adverse events of special interest (AESI) will be summarized by risk group and preferred term defined below. AESIs in RDC clinical database and serious AESI in ARGUS safety database will also be listed.

Adverse events of special interest (AESI) are defined as events (serious or non-serious) which are ones of scientific and medical concern specific to the sponsor's product or program, for which ongoing monitoring and rapid communication by the investigator to the sponsor may be appropriate. Such events may require further investigation in order to characterize and understand them.

Adverse events of special interest are defined on the basis of an ongoing review of the safety data. AESIs are discussed in detail in the Investigator Brochure.

In addition to all serious adverse events reported on a continuous basis throughout the study, the investigator should use the SAE form to report the following medically significant potential risks noted in the Novartis Risk Management Plan for everolimus:

- Development toxicity
- Reproductive (teratogenicity) toxicity
- Intestinal obstruction /ileus
- Male infertility
- Pancreatitis
- Cholelithiasis
- Muscle-wasting/Muscle-loss

All AESIs are defined through the use of MedDRA terms, Standardized MedDRA Queries (SMQ), Preferred Terms (PT), System Organ Classes (SOC), or through a combination of these components. At the project level, a SAS dataset named Case Retrieval Strategy (eCRS) contains the exact composition of the adverse events groupings will be used to map reported adverse events to the adverse events groupings of special interest. This dataset may be updated (i.e., it is a living document) based on review of accumulating trial data, and it is the most up to date version at the time of DBL that will be used. Safety topics flagged in the

eCRS are adjusted to use RMP update flag (RM) instead of core safety flag (SP), with 2 study-specific groupings of “Cholelithiasis” and “Intestinal obstruction ileus” using other flag (OS) to generate protocol-defined AESIs from both RDC clinical and ARGUS safety databases. Note that certain adverse events may be reported within multiple groupings.

For each specified AESI, the number and percentage of patients with at least one event of the AESI occurring during the on-treatment period will be summarized. Summaries of these AESIs will be provided grouped by CTCAE grades, relationship, leading to treatment discontinuation, resulting in dose adjustment/interruption, etc.

### **2.8.3 Deaths**

CTC Grade 5 will not be used in this study; rather, information about deaths will be collected on the CRF End of Treatment (EOT) page. Deaths reportable as SAEs will be listed by patient and tabulated by type of adverse event.

All deaths will be summarized. Following summaries will be provided:

- On-treatment death in RDC clinical database by primary system organ class and preferred term
- All deaths in ARGUS safety database by system organ class and preferred term

Listing of all deaths in ARGUS safety database will also be provided.

### **2.8.4 Laboratory data**

Lab data of hepatic laboratory values will be listed only when DILI cases occur.

### **2.8.5 Other safety data**

Pregnancy test results for safety monitoring is collected locally and will be listed.

Following liver event data will be listed only when DILI cases occur.

- Related imaging of liver event
- Pathology of liver event
- Overview of liver event
- Liver event associated with clinical signs/symptoms
- Potential impact of alcohol use of liver event

## **2.9 Pharmacokinetic endpoints**

Not applicable.

## **2.10 PD and PK/PD analyses**

Not applicable.

## **2.11 Patient-reported outcomes**

Not applicable.

## **2.12 Biomarkers**

Not applicable.

## **2.13 Other Exploratory analyses**

No exploratory analyses are planned.

## **2.14 Interim analysis**

No interim analyses are planned for this study. Nevertheless it may be possible that different analyses may be necessary to descriptively summarize patients on drug at regular intervals.

## **3 Sample size calculation**

The sample size is not based on any statistical considerations.

The purpose of this study is to allow continued use of everolimus in patients who are currently receiving everolimus treatment in a Novartis-sponsored, Oncology Clinical Development & Medical Affairs (CD&MA) study that has reached its study objectives, are not progressing on the current study treatment as defined by the parent protocol and are unable to access everolimus treatment outside of a clinical study.

The total sample size will be determined by the number of patients entering the study.

## **4 Change to protocol specified analyses**

No change from protocol specified analysis is planned.

## **5 Appendix**

### **5.1 Imputation rules**

Not applicable.

#### **5.1.1 Study drug**

Not applicable.

#### **5.1.2 AE date imputation**

Not applicable.

### **5.1.3 Concomitant medication date imputation**

Not applicable.

#### **5.1.3.1 Prior therapies date imputation**

Not applicable.

#### **5.1.3.2 Post therapies date imputation**

Not applicable.

#### **5.1.3.3 Other imputations**

Not applicable.

## **5.2 AEs coding/grading**

AEs will be coded using the latest MedDRA version available at time of database lock while National Cancer Institute Common Terminology Criteria for Adverse Events (NCI CTCAE) version 4.03 will be used for reporting AE severity.

The CTCAE represents a comprehensive grading system for reporting the acute and late effects of cancer treatments. CTCAE grading is by definition a 5-point scale generally corresponding to mild, moderate, severe, life threatening, and death. This grading system inherently places a value on the importance of an event, although there is not necessarily proportionality among grades (a grade 2 is not necessarily twice as bad as a grade 1).

CTCAE grade 5 (death) will not be used in this study; rather, this death information will be collected on the EOT CRF page (Panel: CMP). Grading is applicable in data collected in RDC clinical database but not ARGUS safety database.

The rule for the calculation of the number of occurrences that is provided in the summary of serious and non serious adverse events required for the legal requirements of ClinicalTrials.gov and EudraCT is the following:

If for a same patient, several consecutive AEs (irrespective of study treatment causality, seriousness and severity) occurred with the same SOC and PT:

- a single occurrence will be counted if there is  $\leq 1$  day gap between the end date of the preceding AE and the start date of the consecutive AE
- more than one occurrence will be counted if there is  $> 1$  day gap between the end date of the preceding AE and the start date of the consecutive AE

For occurrence of SAE, the presence of at least one SAE / SAE suspected to be related to study treatment / non SAE has to be checked in a block e.g., among AE's in a  $\leq 1$  day gap block, if at least one SAE is occurring, then one occurrence is calculated for that SAE.

## **5.3 Laboratory parameters derivations**

Not applicable.

## **5.4 Statistical models**

### **5.4.1 Primary analysis**

Not applicable.

### **5.4.2 Key secondary analysis**

Not applicable.

## **5.5 Rule of exclusion criteria of analysis sets**

Not applicable.

